**Impact of Environmental Nudges on Dietary Quality
Hypotheses and Analytic Plan
NCT06119165
Version Date: 10/25/23**

Hypotheses

The overall purpose of this study is to evaluate the impact of a suite of environmentally focused nudges on the nutritional quality of consumers' food selections.

Primary Outcome

The primary outcome is the healthfulness of product selections, operationalized as Nutri-Score scores.

We hypothesize that compared to the control arm (no eco-labels, swaps, or peer comparisons on products), the experimental arm (eco-labels, swaps, and peer comparisons on products) will lead to improved healthfulness of product selection.

Secondary Outcomes

The secondary outcomes are as follows: carbon footprint of selections [operationalized as products' greenhouse gas emissions (GHGE) per 100g]; acceptability of eco-labels, swaps, and peer comparisons; thinking about health, cost, taste, and environmental sustainability during the shopping task; perceived healthfulness and sustainability of sustainable and unsustainable items; purchase intentions for sustainable and unsustainable items; injunctive norms; and descriptive norms.

We hypothesize that the experimental arm will lead to:

Environmental

- A) Lower carbon footprint from selections (operationalized as GHGE per 100g)

Psychological

- B) Higher acceptability of eco-label intervention
- C) Higher acceptability of swaps intervention
- D) Higher acceptability of peer comparison intervention
- E) Higher thinking about the health of food products
- F) Higher thinking about cost of food products
- G) Higher thinking about taste of food products
- H) Higher thinking about environmental sustainability of food products
- I) Higher perceived healthfulness of sustainable items
- J) Higher perceived sustainability of sustainable items
- K) Lower perceived healthfulness of unsustainable items
- L) Lower perceived sustainability of unsustainable items
- M) Higher intention to purchase sustainable items
- N) Lower intention to purchase unsustainable items
- O) Stronger injunctive and descriptive norms to buy sustainable items

Statistical Considerations

Statistical Methods

The study is a randomized controlled trial. The analysis will rely on random assignment to identify the effect of front-of-package eco-labels, swaps, and peer comparisons on consumer choices compared to the control arm.

We will descriptively report unadjusted values for primary and secondary outcomes. We will use a two-sided critical alpha of 0.05 to conduct all statistical tests. Per CONSORT guidelines, we will not test for balance in covariates but will describe participant characteristics by trial arm. Primary analyses will be intent-to-treat, including all eligible participants with non-missing data for the outcome being analyzed.

For the primary, secondary, and other outcomes, we will assess whether the outcomes vary by study arm using linear regressions.

Because all analyses are pre-specified and each analysis only compares treatment to control (vs. comparing multiple treatment arms to one another), we do not plan to adjust analyses for multiple comparisons.

Exploratory Analyses

We will examine whether the following participant characteristics moderate the intervention effects on the primary outcome:

- a. Gender
- b. Educational attainment
- c. Income
- d. Frequency of red meat intake
- e. Political orientation
- f. Interest in sustainability

To test whether these characteristics moderate the effect of each intervention on healthfulness of product selection, we will fit a series of linear regression models (one for each potential moderator), with trial arm, the moderator, and their interaction as predictors.

Sample Size and Power

This is the first study to our knowledge to test the effects of environmental nudges on healthfulness of food selections. Thus, we powered the study to detect a small standardized effect of Cohen's $d=0.15$. The target sample size of 2,000 (1,000 per arm) provides 90% power to detect a difference in means between the experimental and control arms of $d=0.15$ or larger, assuming $\alpha=0.05$.

Outliers and Exclusions

The response scale does not permit outliers. We will exclude participants who complete the survey in $<1/3$ of the median completion time.

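### Can acceptability of the nudges be compared between arms when the control arm shops without them?

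*SAP*

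**What the plan says.** Under Primary Outcome, the SAP sets up its hypothesis "compared to the control arm (no eco-labels, swaps, or peer comparisons on products") and describes the other group as "the experimental arm (eco-labels, swaps, and peer comparisons on products"). The arms therefore differ in what is displayed on the products.

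Under Secondary Outcomes it lists "acceptability of eco-labels, swaps, and peer comparisons" among the outcomes. The lettered hypotheses share one stem, "We hypothesize that the experimental arm will lead to". Below it stand B, "Higher acceptability of eco-label intervention"; C, "Higher acceptability of swaps intervention"; and D, "Higher acceptability of peer comparison intervention".

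Statistical Methods gives one inferential rule for all outcomes: "For the primary, secondary, and other outcomes, we will assess whether the outcomes vary by study arm using linear regressions". The same section says that unadjusted values of the primary and secondary outcomes will be reported descriptively, and that each analysis includes the eligible participants who have data on the outcome concerned.

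**The concern.** Most secondary outcomes concern things that both arms meet: food products, the thoughts that come up while shopping, purchase intentions, norms. B to D are different. They ask for a rating of the intervention itself, and the control arm shops without it. Two difficulties suggest themselves.

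- Control participants might have no rating at all. Only the experimental arm would then enter the analysis, and an arm coefficient could not be estimated.
- Control participants might rate nudges that they did not meet while shopping. The contrast would then set experienced against hypothetical nudges.

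In the second case, a higher mean in the experimental arm would not show that people accept the nudges: both arms could dislike them, one slightly less. Equal means would not show the opposite: both arms could like them very much. If the arm contrast were the plan's only evidence on whether shoppers accept these nudges, three secondary outcomes would be tested in a way that misses their purpose, and readers could draw the wrong conclusion in either direction.

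**Working it through.** **1. How many outcomes are involved.** Counted from Secondary Outcomes: carbon footprint 1, acceptability 3, thinking 4, perceptions 4, intentions 2, norms 2. The sum is 1 + 3 + 4 + 4 + 2 + 2 = 16. Three of 16 is 19%. This counts the outcomes in question; it does not measure an error.

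**2. The plan's own figure.** Sample Size and Power states 90% power for d = 0.15 with 1,000 per arm and alpha 0.05; Statistical Methods makes the tests two-sided.

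- Standard error of the difference in SD units: √(2/1000) = 0.0447
- Standardised difference: 0.15/0.0447 = 3.354
- Power: Φ(3.354 − 1.960) = Φ(1.394) = 0.918

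The stated 90% is met. Nothing in the concern touches this figure.

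**3. What the arm contrast can and cannot show.** The SAP gives no acceptability scale. Assume, for illustration only, a 1 to 5 scale with SD 1.

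| Control mean | Experimental mean | Difference | Chance of a significant result |
|---|---|---|---|
| 1.50 | 1.65 | 0.15 | 91.8% |
| 4.20 | 4.35 | 0.15 | 91.8% |
| 4.20 | 4.20 | 0 | 5% |

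The first two rows give the same test although the levels are far apart. The third gives a null although both arms rate the nudges highly. So the contrast alone says nothing about the level. That part of the reasoning is correct.

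**4. Whether the plan asks the contrast for the level.** The stem of B to D is causal and comparative: being in the experimental arm is predicted to raise the rating. The estimand that matches it is the difference in mean rating between randomised arms, and a linear regression on arm estimates that. The SAP contains no sentence that makes B to D a demonstration of absolute acceptability, no acceptability threshold, and no rule that turns a null into a verdict of unacceptable.

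**5. Where the level appears.** Acceptability is a listed secondary outcome, so the unadjusted values promised in Statistical Methods include it. A reader who sees 1.50 and 1.65, or 4.20 and 4.20, can tell the rows of the table apart. With about 1,000 participants in the experimental arm, a 95% interval for its mean would have half-width 1.96/√1000 = 0.062 SD, so the reported value would be precise.

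**6. Whether control ratings can exist.** The control definition is limited to what is shown on products. Outliers and Exclusions refers to a survey that participants complete. A control participant can be asked there about a label, a swap or a peer comparison that is described or displayed. Since the SAP regresses every secondary outcome on arm, the natural reading is that both arms give these ratings. The contrast is then the randomised effect of having shopped with the nudges on how they are rated, which is what B to D predict.

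**The case for a change.** The strongest case for the concern is that it does not depend on the measurement procedure. Even if control participants are shown the nudges after shopping, the contrast remains an effect of exposure on attitude. The SAP attaches no confidence interval, benchmark or interpretive criterion to the level in the exposed arm. An unsupported hypothesis of higher acceptability could be reported although exposed shoppers rated the nudges very favourably. And an estimand belongs in the SAP.

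Some of this stands. An arm contrast carries no information on the absolute level, and the SAP does not say what control participants rate.

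Neither point shows an error. An exposure effect is what the wording under Secondary Outcomes already claims, so the estimand is stated and the test fits it. What control participants are shown, and when, is the kind of detail that a protocol commonly holds, and the protocol is not at hand. A one-arm interval would be a useful addition, but a test against a scale midpoint would bring in a scale that the SAP does not describe and a threshold that it does not adopt. Taking B to D out of the arm regressions would discard three valid pre-specified randomised comparisons. The feared misreading is a risk in later reporting; no rule in the plan prescribes it.

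**Conclusion.** The concern does not hold. B to D predict a difference between randomised arms, and the planned regression on arm tests that difference. The level of acceptability is a separate question, which the promised descriptive values cover. The possibility that the arm coefficient cannot be estimated is conjecture, because shopping without the nudges does not prevent rating them in the survey. Three of 16 secondary outcomes are concerned, none is given a wrong analysis, and the primary outcome and the stated power are unaffected.

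This rests on one assumption that the SAP does not spell out: that both arms give the acceptability ratings. The single rule of regressing every secondary outcome on arm points that way. If the protocol collected these ratings in the experimental arm only, the contrast for B to D could not be estimated and the conclusion would change for those three outcomes.

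### Does the moderator analysis promise effects of the individual nudges that a two-arm design cannot separate?

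*SAP*

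**What the plan says.** The Hypotheses section gives the study's purpose as to "evaluate the impact of a suite of environmentally focused nudges on the nutritional quality of consumers' food selections". The primary hypothesis has two arms: "the experimental arm (eco-labels, swaps, and peer comparisons on products" is set against a control arm that has none of the three nudges.

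Statistical Methods confirms that "each analysis only compares treatment to control (vs. comparing multiple treatment arms to one another".

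Exploratory Analyses opens with "We will examine whether the following participant characteristics moderate the intervention effects on the primary outcome" and lists six characteristics: gender, educational attainment, income, frequency of red meat intake, political orientation and interest in sustainability. The next sentence states the aim as "To test whether these characteristics moderate the effect of each intervention on healthfulness of product selection". It then specifies a separate linear regression for each moderator, "with trial arm, the moderator, and their interaction as predictors".

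**The concern.** The word *each* implies more than one intervention. It cannot mean several treatment arms, because there is only one. The SAP also offers another reading: under Secondary Outcomes, hypothesis B is "Higher acceptability of eco-label intervention", and C and D name the swaps and the peer comparison as interventions in the same way. In that vocabulary, the moderator sentence sets out to learn whether, say, political orientation alters the effect of eco-labels as distinct from swaps.

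The design cannot answer that question. If the sentence governed the analysis, the plan would be committed to effects that cannot be estimated. A significant interaction might then be presented as pre-specified evidence about a single nudge when it concerns the package. This deserves a check, because asking which component did the work is natural after a multi-component trial, and because the SAP relies on pre-specification to justify leaving multiplicity unadjusted.

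**Working it through.** **1. The plan's own figure.** Inputs from Sample Size and Power: 1,000 per arm, d = 0.15, α = 0.05; the two-sided test is from Statistical Methods.

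- Power = Φ(d·√(n/2) − 1.960) = Φ(0.15 × √500 − 1.960) = Φ(3.354 − 1.960) = Φ(1.394) = 0.918. The noncentral t distribution also gives 0.918.
- For exactly 90% power, n per arm = 2 × (1.960 + 1.282)² / 0.15² = 934 after rounding up, so 1,000 per arm is enough.

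The stated 90% is reproduced. It concerns the package against control and does not involve the moderator wording.

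**2. What a component-level analysis would need.** Let A be the arm indicator, M the moderator, and E, S and P the indicators for eco-label, swap and peer comparison. The arm definitions give E = S = P = A for every participant. A component model would be

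Y = β0 + β1·E + β2·S + β3·P + γ·M + δ1·E·M + δ2·S·M + δ3·P·M.

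Substituting A for E, S and P gives

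Y = β0 + (β1 + β2 + β3)·A + γ·M + (δ1 + δ2 + δ3)·A·M.

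Only the two sums can be estimated. A numerical check with 1,000 per arm and a binary moderator (binary is an assumption) gave rank 4 for the 8 columns. The identification argument is therefore correct, and a larger sample would not alter it.

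**3. What the SAP actually specifies.** Its model has an intercept, A, M and A·M. In the same check it has rank 4 for 4 columns, so it is fully estimable. With a binary moderator, the interaction coefficient is the arm difference at M = 1 minus the arm difference at M = 0, which is moderation of the package. A moderator with more categories adds interaction columns, but they are still arm-by-moderator terms and have the same meaning.

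**4. Counting.** One model for each of 6 moderators gives 6 arm-by-moderator analyses. A literal component reading would need 6 × 3 = 18. The SAP's provision of one model per moderator, with trial arm as the only treatment term, matches the first count and leaves no room for the second.

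**5. The statements side by side.** The purpose refers to a suite. The primary hypothesis contrasts all three nudges with none. Statistical Methods limits every analysis to treatment against control. The lead-in to the moderator list speaks of intervention effects without *each*. The moderator model has arm as its treatment term. Only the single phrase in the aim sentence points the other way.

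**The case for a change.** The strongest case for a change is that the sentence is wrong on either reading. If the sponsor meant the package, the word *each* is an error. If the sponsor meant the components, the aim is impossible. Hypotheses B to D show that the component reading is not far-fetched, because the SAP does call individual nudges interventions. The Statistical Methods sentence listing the three nudges does not itself say whether their effect is joint or separate. Since multiplicity is left unadjusted on the ground that everything is pre-specified, the stated question should match the fitted model. The remedy would be a few words.

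Part of this stands: the phrase does not fit the design, and no regression on these data could deliver what it literally says. The rest carries less weight.

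- Hypotheses B to D concern participants' acceptability ratings of each nudge. They are separate outcomes, not component effects on Nutri-Score, and do not show that component effects on product selection were intended.
- What is pre-specified for computation is the model, and it is unambiguous. An analyst who follows it obtains package-level moderation and nothing else.
- The SAP has no rule for reporting an interaction as belonging to one nudge. Misattribution is possible in the write-up of any bundled intervention, and it would contradict this SAP's own statement that its analyses compare treatment with control.
- That opposing component effects could cancel is true of every bundled intervention. It is a remark about the choice of design and does not show an error in the analysis plan.

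**Conclusion.** The concern does not call for a change to the plan. The phrase about each intervention is a clerical slip: it occurs once, in an exploratory section, and the model specification in the same sentence corrects it in practice. All six planned models are estimable and answer a clear question, namely whether the effect of the combined suite against control varies with the characteristic. Rewording would change none of the models, estimates, α, sample size or power (91.8% recomputed against 90% stated). The contrast it would spell out is already plain from the purpose, the primary hypothesis and Statistical Methods.

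This conclusion rests on two assumptions: that the analyst fits the models as specified, and that the results are described as differences between the experimental and control arms. Both follow from the SAP as written. If a report did attribute an interaction to a single nudge, the fault would lie in the report, and the SAP's own arm definitions would show it.

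### The SAP names no variance estimator for the six exploratory moderator models; with default standard errors the interaction tests may miss the 5% level if Nutri-Score variance differs between moderator levels of unequal size

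*SAP*

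**What the plan says.** Under Statistical Methods, the SAP sets one error rate for everything: "We will use a two-sided critical alpha of 0.05 to conduct all statistical tests". For the arm comparisons it says "we will assess whether the outcomes vary by study arm using linear regressions", and it adds that "we do not plan to adjust analyses for multiple comparisons".

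Under Exploratory Analyses it lists gender, education, income, red meat frequency, political orientation and interest in sustainability as possible moderators of the effect on the primary outcome. For these, "we will fit a series of linear regression models (one for each potential moderator"), "with trial arm, the moderator, and their interaction as predictors".

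Under Sample Size and Power, "The target sample size of 2,000 (1,000 per arm) provides 90% power" for a standardized difference of 0.15, so allocation is planned as 1:1.

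The SAP does not name a variance estimator for any model, makes no statement about equal variances, and does not give the coding or expected size of the moderator categories.

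**The concern.** Linear regression without further qualification is normally run with model-based standard errors, which assume one residual variance for all participants. Randomization to two equal arms makes that assumption nearly harmless for a comparison of arms. It gives no such protection to an interaction: it balances the arms within each moderator level, but it does not make the levels equal in size or in spread.

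If the smaller level is the more variable one, the pooled standard error of the interaction is too small and moderation may be declared too often. If the smaller level is the less variable one, the standard error is too large and real moderation may be missed. At stake are the nominal 0.05 level and the confidence interval coverage of the six moderator analyses.

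**Working it through.** **Inputs from the SAP.** N = 2,000, 1,000 per arm; two-sided alpha 0.05; d = 0.15; one model per moderator with arm, moderator and interaction.

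**Assumptions, because the SAP gives no figures.** A two-level moderator; a smaller level with share q and residual variance s1²; the rest with share 1−q and residual variance s0²; arms split 1:1 within each level.

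**1. The plan's own figure.** 0.15/√(2/1000) = 3.354, and 3.354 − 1.960 = 1.394, so power is Φ(1.394) = 91.8%. The stated 90% is met (934 per arm would suffice). Sample size is not at issue.

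**2. Arm comparison.** With n per arm and arm variances vA and vB, the pooled variance of the difference is [(vA + vB)/2] × (2/n) = vA/n + vB/n, which is the true variance. Equal arms therefore protect this test.

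**3. Interaction.** This is the arm effect in the smaller level minus the arm effect in the rest.

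- True variance: 4·s1²/(Nq) + 4·s0²/(N(1−q))
- Pooled variance: [q·s1² + (1−q)·s0²] × [4/(Nq) + 4/(N(1−q))]
- Ratio R, pooled to true: [q·s1² + (1−q)·s0²] / [(1−q)·s1² + q·s0²]
- Actual two-sided error: 2·(1 − Φ(1.96·√R))

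R equals 1 if q = 0.5 or if s1² = s0², and otherwise not.

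Example with q = 0.2 and s1²/s0² = 2 (s0² = 1): pooled 1.2 × (4/400 + 4/1600) = 1.2 × 0.0125 = 0.0150; true 8/400 + 4/1600 = 0.0225. R = 0.667, √R = 0.816, and the actual error is 11.0%.

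| q | s1²/s0² | R | √R | Actual error |
|---|---|---|---|---|
| 0.2 | 1 | 1.00/1.00 | 1.000 | 5.0% |
| 0.2 | 1.2 | 1.04/1.16 | 0.947 | 6.3% |
| 0.2 | 1.5 | 1.10/1.40 | 0.886 | 8.2% |
| 0.2 | 2 | 1.20/1.80 | 0.816 | 11.0% |
| 0.2 | 0.5 | 0.90/0.60 | 1.225 | 1.6% |
| 0.3 | 2 | 1.30/1.70 | 0.874 | 8.7% |
| 0.3 | 0.5 | 0.85/0.65 | 1.144 | 2.5% |
| 0.5 | any | equal | 1.000 | 5.0% |

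**4. Simulation, N = 2,000.** With 4,000 runs per case and q = 0.2:

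| s1²/s0² | Pooled SE | HC3 |
|---|---|---|
| 2 | 11.2% | 4.7% |
| 1.5 | 8.3% | 5.0% |
| 0.5 | 1.3% | 4.4% |

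The Monte Carlo standard error near 5% is √(0.05 × 0.95/4000) = 0.34 points, so the HC3 results are compatible with 5%. In a separate set of 6,000-run simulations with other subgroup splits and SD ratios, the pooled arm comparison stayed between 4.4% and 5.2%. When only the arms differed in spread (SD ratio 1.5, q = 0.2), the pooled interaction test ran at 5.5%, close to nominal, because each level is itself split about 1:1.

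**5. Cost of HC3 if variances are equal.** In this four-cell model the expected HC3 variance is the sum of s²/(n−1) over cells, against a true value of the sum of s²/n. With q = 0.2 the cells hold 200, 200, 800 and 800 participants. In units of s², 2/199 + 2/799 = 0.012553, against 2/200 + 2/800 = 0.012500. The standard error is larger by a factor √(0.012553/0.012500) = 1.002, about 0.2%.

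**The case against.** The strongest reply is that the SAP has not chosen wrongly; it has not chosen at all. A linear regression with HC3 standard errors would comply with the text as it stands. That is right. A reader might infer that the plan prescribes pooled-variance standard errors, but that is only the default reading of the term.

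A reader might also infer that unequal subgroup size alone spoils the test, or that the 0.05 level does not hold for the moderator claims. Neither is supported. With equal variances the test is at 5% for any split, and nothing in the SAP shows that Nutri-Score spread differs by any of the six characteristics. The most that can be said is that the level may not hold.

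Three further limits stand. Mild differences do little: at a 20/80 split with an SD ratio of 1.1, the error is 6.4% or 3.8%, depending on which level is more variable. The two-level formula is a simplification, since most of the moderators may have several levels or be continuous. And the analyses are labelled exploratory; six unadjusted tests, if independent, already carry a 1 − 0.95⁶ ≈ 26% chance of at least one false positive.

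What the reply does not remove is that the SAP applies 0.05 to all tests while leaving open the one setting that can move these six away from it, and that setting can be fixed in advance at almost no cost.

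**Conclusion.** The point holds as a conditional one. If the moderator models are run with default standard errors, and if Nutri-Score variance differs between levels of unequal size, the interaction tests depart from 5% in either direction. Over variance ratios of 0.5 to 2, the actual error runs from about 1.6% to 11.0% with a 20% subgroup and from about 2.5% to 8.7% with a 30% subgroup. The shares, the variances and the two-level coding are assumptions; the direction and size for any given moderator cannot be known from the SAP.

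The primary analysis and the other arm comparisons are not affected, provided the analysed arms stay close to 1:1. The stated power is also sound. This is a minor, optional improvement to exploratory analyses.

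**What to change.** Under Exploratory Analyses, after the sentence that describes the moderator models, add: *Interaction tests and their confidence intervals will use heteroscedasticity-consistent (HC3) standard errors.*

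This takes one sentence and one software option, with no new data and no change to the sample size. The price is the 0.2% in standard error worked out above if variances are equal. The arm-only models need no change; HC3 may be used there for uniformity, but nothing depends on it.

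### Do the no-outlier sentence and plain linear regression put the Nutri-Score and GHGE analyses at risk?

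*SAP*

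**What the plan says.** Under Primary Outcome: "The primary outcome is the healthfulness of product selections, operationalized as Nutri-Score scores". Under Secondary Outcomes, the carbon footprint of selections is measured as "greenhouse gas emissions (GHGE) per 100g" of the products. The other secondary outcomes are psychological measures such as acceptability, thinking, perceptions, intentions and norms.

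Under Statistical Methods, one model serves them all: "For the primary, secondary, and other outcomes, we will assess whether the outcomes vary by study arm using linear regressions". The same section defines who is analysed: "Primary analyses will be intent-to-treat, including all eligible participants with non-missing data for the outcome being analyzed". It also sets the test level: "We will use a two-sided critical alpha of 0.05 to conduct all statistical tests".

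Sample Size and Power gives 1,000 participants per arm and 90% power for a standardised mean difference of 0.15. Outliers and Exclusions has two sentences. The first is "The response scale does not permit outliers". The second removes participants who finish in under a third of the median time.

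**The concern.** Three things look wrong on a first reading.

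- **The outlier sentence is unqualified.** It suits rating items. A product's emissions per 100g are not an answer on a response scale, so the reason given for having no outlier rule does not cover that outcome. The same applies to Nutri-Score, which is also a product attribute.
- **The unit of analysis is not spelled out.** Both product outcomes are described in the plural, which suggests several selections per shopper. The SAP names no per-participant mean or sum, no clustered standard error and no random intercept. An ordinary regression on product rows would treat one shopper's items as independent, and the primary test would be too liberal.
- **GHGE may be right-skewed.** If so, a few high-emission choices could weigh heavily on the mean difference and cost power, and no log-scale or trimmed analysis is planned.

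At stake would be the validity of the single primary test and the precision of the first-listed secondary outcome.

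**Working it through.** **1. The plan's own figure.** Inputs from Sample Size and Power: n = 1,000 per arm, d = 0.15, α = 0.05; two-sided from Statistical Methods. Power ≈ Φ(d·√(n/2) − 1.96) = Φ(0.15·√500 − 1.96) = Φ(3.354 − 1.96) = Φ(1.394) = 0.918. The stated 90% is met, with one independent value per participant as its basis.

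**2. If product rows were analysed by ordinary regression.** The SAP gives neither the number of items m nor the intraclass correlation (ICC), so both are assumed. Design effect DE = 1 + (m − 1)·ICC; true type I error = 2·[1 − Φ(1.96/√DE)].

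| m | ICC | DE | True type I error at nominal 5% |
|---|---|---|---|
| 5 | 0.05 | 1.20 | 7.4% |
| 10 | 0.10 | 1.90 | 15.5% |
| 20 | 0.20 | 4.80 | 37.1% |

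With one value per participant, DE = 1 and the error is 5%. The size of the problem therefore depends on which unit the SAP means.

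**3. Which unit the SAP means.** Four statements bear on it:

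- the analysis set consists of participants with a non-missing outcome (Statistical Methods);
- the power calculation counts 1,000 people per arm and a difference in means (Sample Size and Power);
- the moderators are participant characteristics (Exploratory Analyses);
- the exclusion rule removes participants (Outliers and Exclusions).

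No statement makes the product a row. The plural wording describes what is scored, not the level at which it is analysed.

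**4. Validity under skew.** The SAP gives no GHGE distribution, so log-normal data were assumed: two-sample t-test, 1,000 per arm, 3,000 replicates, one selection or the mean of five. Simulated type I error was 0.051 to 0.057 for log-SD 0.5 to 1.5. For an extreme log-SD of 2 it was 0.035 to 0.044, which is conservative.

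**5. Power under skew.** Take one log-normal value per person, log-SD 1, and a shift of 0.15 on the log scale. The control coefficient of variation is √(e − 1) = 1.311. Raw-scale d = (1 − e^−0.15) / [1.311·√((1 + e^−0.30)/2)] = 0.1393/(1.311 × 0.933) = 0.114. Power is Φ(0.114·√500 − 1.96) = 72%, against 92% on the log scale.

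That gap belongs to a single selection per person. With participant means over several items (log-SD 1, ICC 0.10) and the same 0.15 shift, both scales have power of 99.7% or more. With the shift reduced so that power is not saturated, simulation gave 77% against 88% (5 items, shift 0.08) and 75% against 80% (10 items, shift 0.06). The 20-point loss and the within-person correlation problem therefore cannot both be claimed in full: one needs a single item per person, the other needs several.

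**6. Robust standard errors.** With equal arms the pooled variance of the mean difference is [(s₁² + s₂²)/2]·(2/n) = (s₁² + s₂²)/n, which is the unequal-variance expression. At 1:1 allocation, robust standard errors would change almost nothing.

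**The case for a change.** The strongest case for acting is that the model for the one primary test should leave no choice open. Two analysts could fit participant means or product rows and each claim to follow the SAP, and only the first would be valid without clustering. The outlier sentence is also wrong as written for GHGE, and no protocol could make it right. A few added sentences would settle both points and would need no new data.

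Part of this stands. The per-participant summary is not stated, and the sentence does not describe the two product outcomes. But the product-row reading conflicts with every statement in the SAP that identifies who is counted, so it is not an equally open alternative. The details of the shopping task and its scoring commonly sit in the protocol, which is not at hand. The outlier sentence prohibits no diagnostic or sensitivity analysis. Its practical effect is that all values are kept, which is a sound default for an intent-to-treat comparison of means. GHGE values can also come only from the products offered in the task, not from free entry by respondents. A log-scale or winsorised run would be a matter of preference: it concerns a secondary outcome and would leave the raw-scale mean as the main estimate.

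**Conclusion.** The concern does not call for a change. On the reading the SAP supports, one value per participant per outcome, the primary test keeps its 5% level and the stated power holds at 91.8%. The inflation of 7% to 37% needs three assumptions the SAP does not make: product rows, an item count and an ICC. Assumed skew in GHGE leaves the type I error close to nominal at this sample size (0.051 to 0.057 for log-SD 0.5 to 1.5). The power loss from 92% to 72% rests on an assumed distribution and a single selection per person.

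Two small imperfections remain: a summary step that analysts would fill sensibly, for example by averaging over selected products, and an outlier sentence worded too broadly. Tidying either would alter no planned result. The conclusion would change only if the analysis were in fact run on product rows without allowing for clustering, and nothing in the SAP says that it will be.
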